Research Summary

1. Protocol Title:

Effects of Lavender Oil on Postoperative Pain, Sleep Quality and Mood.

2. Purpose of the Study:

The purpose of this study is to evaluate the integration of lavender essential oil in surgical patients during the perioperative and postoperative phase of care. The study will assess patients' pain, sleep quality, and mood. The goal is to support that lavender oil will decrease pain scores and narcotic use, increase sleep quality, and decrease anxiety by improving overall patient satisfaction and supporting their natural sense of well-being. This research project will help support the use of complementary medicine in a hospital setting. The increased awareness and use of complementary medicine in a hospital setting will strengthen the patient centered care model that all hospitals strive to achieve.

3. Background & Significance:

Essential oils have been formally documented in use since the time of the Egyptians. The Ebers Papyrus document notes Egyptians using frankincense for different physical ailments [1]. In Greece Hippocrates used essential oils to fumigate the city of Athens to fight off the plague [1]. In medieval periods lavender essential oil was used for its antidepressive, anxiolytic, sedative, and analgesic properties. Medieval Persian physicians made records of their treatment plans which included lavender for depression and pain for headaches [2,3]. With the invention of steam distillation to separate the essential oil from the plant Europe began to use oils in perfumes and for medicinal benefits in the 1500's. Two physicians named Hieronymus and Brunschwig wrote one of the earliest printed books on the distillation and use of essential oils for medical benefits [4]. By the 19th century a French chemist Rene- Maurice Gattefosse was known for studying essential oils and their therapeutic benefits. His work and documentation led the way for the support of essential oil in medical ailments. Robert Tisserand in the early 1990s reviewed the French chemists work and added to his research to help make essential oils more known to the public in present day [1].

In recent years lavender has been studied on human subjects to tests its known reputation for sedative, anxiolytic, and analgesic properties. In one clinical trial oral administration of lavender was compared to Ativan 0.5mg for generalized anxiety disorder. The study supported that the oral lavender oil called Silexan was as effective as 0.5mg of Ativan in adults with generalized anxiety disorder [5]. A second clinical trial analyzing sleep quality found that ischemic heart patients in the intensive care unit received better sleep with 100% lavender oil undiluted placed on a cotton ball within 20cm from the patient from the hours of 9pm-6am [6]. Two studies have used lavender oil through inhalation in the recovery room with an oxygen mask after surgery for pain control. The first study was patients after breast biopsy, the second was patients who just had laparoscopic adjustable gastric banding [7,8]. The study with the breast biopsy patients showed a higher satisfaction rate with pain. The patients undergoing laparoscopic banding also showed a higher rate of satisfaction with pain as well as decreased opioid use in the recovery room. Furthermore one study used 100% lavender oil undiluted on the skin of pediatric patients undergoing tonsillectomy as a topical application and asked the patients to inhale. The study showed a decrease use in Tylenol usage postoperatively [9].

4. Design & Procedures:

Design

Randomized study with control group and test group. Using a 1:1 treatment allocation ratio, the total of 60 patients (30 per arm) will be randomly assigned to control or treatment arm. The Statistical Investigator will generate the randomization scheme and monitor the randomization process over the course of the trial. The study will use randomization with random permuted blocks. The test group will receive 50% lavender oil diluted in fractionated coconut oil and the control group will have the current standard of care with no essential oil intervention (coconut oil only) will be applied. Fractionated coconut oil is being used because it is colorless, odorless, does not stain clothing, and has a long shelf life. It also serves as a carrier oil for the essential oil to absorb into the skin instead of evaporating off the skin due to essential oils volatile nature.

Study Procedure

The lavender essential oil used will be from the company doTERRA. This essential oil company was chosen because this company has a medical and science governing board made up of physicians, surgeons, chemists and pharmacists. The oil is also third party tested by [name] a trusted chemist in the essential oil community for purity and quality. Gas chromatography and mass spectrometry are used to ensure purity and no unwanted substances are in the essential oil. doTERRA's essential oils have also already been used in a hospital setting at Vanderbilt University hospital in Tennessee. doTERRA's essential oils were diffused in the Vanderbilt ER at the nursing stations. After 3 months of diffusing staff felt less work related stress, less time feeling overwhelmed, and had more energy at work [13].

5. Selection of Subjects:

Potential subjects will be selected from the clinic of [name]. Subjects will be consented by investigators or study key personnel.

Inclusion Criteria:

Women undergoing any form of breast reconstruction therapy Ages 18-85 At least a one night stay in hospital after surgery

Exclusion Criteria:

Sensitivity or allergy to coconut Use of sleeping aide drugs Use of benzodiazepines History of any of the following: asthma, eczema, allergy to flowers, smell disorders Sensitivity to lavender oil or any of its ingredients Pregnant women will be excluded from the study. During routine preoperative testing the patient's menstrual history or urine pregnancy test will be performed to identify any patient who is pregnant.

6. Subject Recruitment & Compensation:

Enrollment goal will be 60 subjects. We anticipate enrolling 60 subjects over 6 months and anticipate the trial to be complete within 1 year. The subjects will not be compensated for the study.

7. **Consent Process** – see Section 14 of the e-IRB submission form and complete the questions in that section.

8. Subject's Capacity to Give Legally Effective Consent:

9. Study Interventions:

After informed consent is obtained, exactly 4 drops of 50% lavender solution will be placed on the wrist over the radial artery. The patient will rub her wrists and hands together and then inhale and exhale slowly for one minute. This will occur thirty minutes before being taken to the operating room. The dilution of 50% was chosen after reviewing Robert Tisserand's book on essential oil safety, consulting a local certified aromatherapist, [name], and consulting [name], executive vice president and chief medical officer of doTERRA essential oils [10]. This percent dilution is recommended on skin and is not likely to cause irritation to the skin. Repeated insult patch skin testing from doTERRA has supported this dilution rate to be safe to the skin. Furthermore a previous study used 100 % lavender oil on children age 5-12 undergoing tonsillectomy with no adverse reactions [9]. The first dose will be given thirty minutes prior to the operating room because it takes 20 minutes for lavender to be absorbed thought the skin and reach peak plasma levels [11,12].

During surgery the patient will receive 4 drops of 50% solution lavender oil on the temple region over the temporal artery every 2 hours until completion of surgery. This will be applied by the anesthesia team. If the temporal region is not accessible the shoulders or feet will be alternate locations of application. When the patient arrives to the recovery room she will receive lavender oil through an oxygen mask. A 50 % solution will be used by placing 4 drops of the lavender solution on the mask and wiping it around the mask with a cotton ball. This delivery method will be used because this was used in a study from New York University Medical Center studying postoperative pain and no adverse events occurred [7]. When the patient is on the post-operative floor she will receive 50 % lavender oil on the wrist every 4 hours in the same manner as preoperatively from the hours of 6am to 9pm. Nightly (9pm-6am), 8 drops of 50% lavender oil will be placed on the cotton ball situated within 20cm of the patient. This method and concentration was chosen after reviewing a study in ischemic heart patients in the intensive care unit. The patients received lavender at bedside on a cotton ball and had statistically significant better sleep quality [6]. The control group will have coconut oil applied without any lavender oil applied in the same sequence as listed above. This will ensure the same procedures are carried out under both arms.

Blood pressure, pulse, respiratory rate, and oxygen saturation will be monitored in the preoperative area before lavender is given and 30 minutes after it is given. The level of pain will also be asked prior to application and at the second set of vitals. The control group will get two sets of vital measurements and pain scale measurements without any intervention. The same vitals will be recorded while the patient is under anesthesia every 30 minutes. There will be a notation in the chart when lavender is given to correlate time from application to time of vitals recorded. A review of the electronic medical record will be done to record amount of narcotic needed interop in both groups.

In the recovery room after the patient is given lavender through the oxygen mask the same vital signs and pain score measurement will be taken 15, 30, and 60 minutes from lavender application. In the control group on arrival to the recovery room the same data points will be

measured with the same time intervals with coconut oil only. The amount of narcotic needed in the recovery room will be taken from the electronic medical record for each group.

Postoperatively on the floor vital signs as noted above will be recorded every 4 hours. At each 4 hour interval after the vital signs are taken lavender will be applied to the experimental group and no intervention in the control group. One more set of vitals signs will be recorded 45min after application of lavender each time lavender is applied. There will be a review of narcotic use from the electronic medical record from both groups. There will be a notation when lavender was given to correlate lavender application and narcotic use.

The anxiety questionnaire will be given preop before the application of lavender and then daily for every post-op day they stay. The questionnaire is called the hospital anxiety and depression scale.

The sleep questionnaire will be given in preop before application of lavender and then daily for every post-op day they stay. The sleep questionnaire is called the Richard Campbell Sleep Questionnaire.

Daily starting on postop day 1 the patient will also record their level of satisfaction of pain control from a scale of 1-10 with 1 being not satisfied and 10 being satisfied. Patients typically stay in hospital 1-3 days post-op. A survey will be filled out daily.

10. Risk/Benefit Assessment:

The use of lavender essential oil could have potential benefits to the patient:

- $\circ~$ Main benefits include decreased pain, better sleep, and better mood.
- o Other benefits include relaxation, calming environment, pleasing aroma.

Risks are minimal, but there is potential for some adverse events:

• Possible side effects include skin irritation or coughing.

- If skin irritation occurs, plain fractionated coconut oil will be applied to dilute the essential oil. Then a 4x4 cotton gauze will be used to wipe off the essential oil. The coconut oil will be applied a second time and then removed by a 4x4. Washing is not a recommend step because water will drive the essential oil into the skin further. If there is still a reaction and the patient is uncomfortable oral Benadryl will be given, 25mg PO Q6hrs prn itching or skin irritation. In the control arm, should the coconut oil irritate the skin it will be removed using a 4 x 4 cotton swab.
- For coughing or any feeling of shortness of breath or chest discomfort, lavender oil therapy will be stopped. Any lavender applied to the skin will be diluted with fractionated coconut oil as mentioned above.
- For any serious, unexpected event, which occurs to any subject during this study the appropriate DUHS IRB Adverse Event notification will be completed, e-signed by the PI and submitted to the DUHS IRB within 5 days of notification of the reported event.
- Any patient who does not want to participate in the study can decline at any time.
- The patient's demographics including name will remain confidential.

11. Costs to the Subject:

Study intervention and Lavender Oil will be provided to subjects at no additional cost. Subjects and/or their regular insurance provider will be responsible for all procedures and tests considered standard of care for their condition.

12. Data Analysis & Statistical Considerations:

Study Design/Endpoints: The primary outcome will be a difference in pain scores between the 2 groups and/or decrease in narcotic use and/or increased patient satisfaction of pain control. Secondary outcomes are better sleep and decreased anxiety.

Analytic Plan and Method: Differences in the change scores of pain in the two groups as well any other demographic and clinical continuous variables will be examined using t-test or Wilcoxon test, depending on whether the variables are normally or non-normally distributed respectively. The differences between the categorical variables will be examined using chisquared or Fisher's exact test. Analysis will be conducted under the intention to treat (ITT). Missing data will be imputed under multiple imputation methods. Differences in the outcomes while controlling for potential covariates (age, etc) will be examined using linear regression. Significance of the tests will be assessed at alpha = 0.05. Analysis will be conducted using SAS 9.4 (SAS Institute, Inc., Cary, NC.).

Power and Sample Size Calculations: A study called the effectiveness of lavender essence on sternotomy related pain intensity after coronary artery bypass grafting evaluated the effectiveness of lavender. The study observed pain scores of 6.45 (SD: 2.23) and 4.11 (2.13) in the control and treatment groups respectively [14]. For 80% power at alpha = 0.05, with the above observed means and standard deviations in the control and treatment groups, 15 subjects per group will be needed. Assuming about a 20% drop-out rate, the study would need 17 subjects per group.

13. Data & Safety Monitoring:

Data and safety monitoring will be reviewed by a team of experts (a least 2 physicians will be identified by the PI in this area of research and who are not associated with this study). Adverse events (AE) and serious adverse events (SAE) will be examined by the committee. We plan to have a review of the safety data in a meeting when half the study subjects are recruited into the study. The committee will decide on the continuity of the trial after reviewing the SAEs while ensuring the safety of the patients.

14. Privacy, Data Storage & Confidentiality – see Section 12 of the e-IRB submission form and complete the questions in that section.

References.

- 1. Jane Buckle. Clinical Aromatherapy Essential Oils in Healthcare. Churchill Livingstone Elsevier;2015.2-13.
- 2. N. Vakili and A. Gorji. Psychiatry and psychology in medieval Persia. *Journal of Clinical Psychiatry*. 2006;67:1862-1869.
- 3. A. Gorji and M.K.Ghadiri. History of headache in medieval Persian medicine. *Lancet Neurology*. 2002;1:510-515.
- 4. Aroma Tools. Modern essentials: a contemporary guide to the therapeutic use of essential oils. Utah: Aroma Tools; 2014. 11 p.
- 5. H. Woelk and S, Schlafke. A multi-center, double-blind, randomized study of the lavender oil preparation silexan in comparison to lorazepam for generalized anxiety disorder. *Phytomedicine*. 2010;17: 94-99.
- 6. Moeini M, Khadibi M, Bekharadi R, et al. Effects of aromatherapy on the quality of sleep in ischemic heart disease patients hospitalized in intensive care units of heart hospitals

of the Isfahan university of medical sciences. *Iranian Journal of Nursing and Midwifery Research*. 2010;15:234-239

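### Any form of breast reconstruction is eligible, but procedure type is not pre-specified in the analysis or the randomization, which costs precision and leaves the comparison open to chance imbalance

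*Combined protocol and SAP*

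**What the plan says.** Section 5 (Selection of Subjects) includes "Women undergoing any form of breast reconstruction therapy". The only other limit on the surgical mix is "At least a one night stay in hospital after surgery".

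Section 4 (Design & Procedures) sets the allocation: "Using a 1:1 treatment allocation ratio, the total of 60 patients (30 per arm) will be randomly assigned". On the method it says "The study will use randomization with random permuted blocks", and it names no stratification factor.

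Section 12 (Data Analysis & Statistical Considerations) states that differences in pain change scores, and other continuous variables, "will be examined using t-test or Wilcoxon test, depending on whether the variables are normally or non-normally distributed respectively". It then adds: "Differences in the outcomes while controlling for potential covariates (age, etc) will be examined using linear regression". Age is the only covariate named, and the list is left open. Procedure type is not mentioned as a stratum, covariate, subgroup or recorded variable.

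Section 9 (Study Interventions) repeats the oil every 2 hours until surgery ends, collects narcotic use during surgery, in recovery and on the floor, and notes "Patients typically stay in hospital 1-3 days post-op".

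**The concern.** Two of the alternative primary outcomes in Section 12, pain and narcotic use, can reasonably be expected to depend on how extensive the operation is. If eligible operations differ in extent, an analysis that ignores the difference leaves that variation in the error term. By chance, one arm may also receive more of the larger operations. With 30 per arm such a split is not rare, and an unadjusted test cannot correct for it.

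The planned regression could address this, but its covariates are not fixed. If procedure type is added only after the data are seen, the adjusted result is less convincing than one from a model named in advance.

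**Working it through.** **Inputs from the documents.** Section 12 gives pain scores of 6.45 (SD 2.23) in controls and 4.11 (SD 2.13) on treatment, 80% power and alpha 0.05 (taken as two-sided). Section 4 gives 30 per arm. The SDs come from one different operation, sternotomy for coronary bypass.

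**Assumptions, because the documents give no figures.** There are two procedure groups. The share p with the larger procedure is 0.3 or 0.5. The gap g in mean pain between groups is 1 or 2 points. The planning SD is treated as the within-procedure SD.

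**1. The plan's own figure.** Difference = 6.45 − 4.11 = 2.34. Pooled SD = √((2.23² + 2.13²)/2) = 2.18. The standardized difference is 2.34/2.18 = 1.07. The two-sample t-test (noncentral t) has power 0.780 at 14 per group and 0.810 at 15, so the stated 15 per group is reproduced. At the planned 30 per arm power is 0.98.

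**2. Variance due to procedure.** Variance = g²·p(1−p); share of total = that / (2.18² + that).
- g = 1, p = 0.3: 0.21/(4.755 + 0.21) = 4.2%; total SD 2.23
- g = 1, p = 0.5: 0.25/(4.755 + 0.25) = 5.0%; total SD 2.24
- g = 2, p = 0.3: 0.84/(4.755 + 0.84) = 15.0%; total SD 2.37
- g = 2, p = 0.5: 1.00/(4.755 + 1.00) = 17.4%; total SD 2.40

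**3. Unadjusted standard error.** SE = SD·√(2/30). This runs from 2.228 × 0.258 = 0.58 to 2.399 × 0.258 = 0.62.

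**4. Chance of imbalance.** A 20-point imbalance is a difference of at least 6 patients between arms of 30.
- Two independent binomial(30, p) counts: 0.120 at p = 0.3 and 0.155 at p = 0.5.
- Fixed mix of 18 or 30 of the 60 patients (hypergeometric): 0.158 and 0.196.

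**5. Shift from such an imbalance.** 0.20 × g = 0.2 points for g = 1 and 0.4 for g = 2. Relative to the SE this is 0.2/0.58 = 0.35 to 0.4/0.62 = 0.65.

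**6. Power for 2.34 points with procedure ignored.** At 30 per arm it is 0.98 for g = 1 and 0.96 for g = 2. At 24 per arm (30 less the 20% dropout) it is 0.94 to 0.95 and 0.91 to 0.92. With a 20-point imbalance against treatment at 30 per arm, the expected difference becomes 2.34 − 0.2 = 2.14 or 2.34 − 0.4 = 1.94, and power is 0.87 to 0.96.

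**7. Smaller effects.** Here 2.18 is taken as the total SD, so the residual SD is 2.18·√(1 − R²), with one degree of freedom lost. At 30 per arm:

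| Variance explained | Detectable difference at 80% power | Power for an illustrative 1.3 points |
|---|---|---|
| Unadjusted | 1.60 | 0.62 |
| 5% | 1.56 | 0.64 |
| 10% | 1.52 | 0.67 |
| 20% | 1.44 | 0.72 |

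These figures cover procedure type alone. Any gain from adjusting for preoperative pain is extra, and the documents give no correlation from which to compute it.

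**The case against.** The strongest reply is that little is at stake. Randomization protects the unadjusted test, and its standard error and type I error already allow for chance imbalance in a factor left out of the model. The noise in step 2 and the shift in step 5 are therefore two views of the same variation and must not be added together. The planned effect keeps power above 80% in every scenario computed. At least 80% of trials would not show a 20-point imbalance. All of this stands, and it limits the point to precision and to credibility in a single trial.

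A reader might infer that the plan excludes procedure type from the analysis. It does not: the open list in Section 12 would permit it, and what is missing is pre-specification. A reader might also infer that the documents show procedure to drive pain, stay or length of surgery. They do not. Section 9 gives a typical stay of 1 to 3 days and a repeat interval during surgery, without linking either to procedure. Recruitment from one clinic and the one-night minimum stay may make the mix narrow, so the procedure effect remains a plausible assumption.

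It is also fair that replacing a t-test or Wilcoxon test with a regression changes the primary analysis, and that linear regression may fit narcotic amounts poorly if they are skewed. The fix has to deal with both.

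**Conclusion.** The point holds as a moderate gap in the analysis plan. Eligibility is broad, the main comparison is unadjusted, and procedure type is not pre-specified. Under the assumed gaps of 1 to 2 points, about 4% to 17% of the variance could be removed, and about 12% to 20% of trials would carry an imbalance worth 0.2 to 0.4 points, or about 0.35 to 0.65 of a standard error. If the clinic's case mix is narrow or the procedures differ by less than a point, the gain is smaller.

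The figures do not support a claim of systematic bias or of inadequate power for the 2.34-point effect. The case for acting is that this effect is large (1.07 SD) and comes from a different operation. A smaller true effect is quite possible, and precision would then matter.

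**What to change.** - Record the planned procedure in a few broad categories, defined by the surgical investigators and fixed for each patient before randomization.
- Make the primary treatment comparison for pain a linear regression of the postoperative score on arm, preoperative pain, age and procedure type. Use the preoperative reading taken before the first application, which Section 9 already collects. Name the postoperative time point, since Section 9 has several.
- Keep the t-test or Wilcoxon test as a supporting analysis.
- Adjust narcotic amount and satisfaction for procedure type and age in the same way, with a transformation or a rank-based version if the data are skewed.
- Replace the open covariate list in Section 12 with these named covariates.

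The cost is one extra chart field, a few degrees of freedom out of 60 patients, and a rewritten analysis paragraph. The randomization can stay as it is: stratifying a trial of 60 is a trade-off, and covariate adjustment recovers most of what matters here.

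### Section 9 gives controls coconut oil at every step, yet says they get no intervention preoperatively and at the 4-hourly floor applications; followed literally, those two settings would be unmatched

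*Combined protocol and SAP*

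**What the plan says.** Section 9 (Study Interventions) first lists the applications in the lavender arm: wrist before surgery, temple during surgery, oxygen mask in the recovery room, wrist every 4 hours by day on the floor, and a cotton ball at night. It then sets a general rule for the other arm: "The control group will have coconut oil applied without any lavender oil applied in the same sequence as listed above". The reason follows: "This will ensure the same procedures are carried out under both arms".

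The measurement text after that describes controls setting by setting. Preoperatively: "The control group will get two sets of vital measurements and pain scale measurements without any intervention". In the recovery room, controls are measured at the same intervals, with coconut oil named. On the floor, after each 4-hourly set of vital signs, "lavender will be applied to the experimental group and no intervention in the control group".

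Two other places bear on the control arm. Section 4 (Design & Procedures) describes it as standard care with no essential oil, only coconut oil being applied. Section 10 (Risk/Benefit Assessment) says what to do if coconut oil irritates a control patient's skin.

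**The concern.** The preoperative and floor sentences, taken as written, contradict the general rule. The application is more than a vehicle for oil: the patient rubs her wrists and hands and breathes slowly for a minute, and a member of staff attends. If controls get none of this in two settings, any lavender effect there is mixed with the effect of a short relaxation exercise and extra contact.

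The outcomes exposed are the daily rating of satisfaction with pain control, which Section 12 makes part of the primary outcome, and the daily anxiety questionnaire, a secondary outcome. Requests for narcotics, also part of the primary outcome, are possibly exposed. If staff differ in how they read the sentences, the comparator would also vary between patients and could not be described accurately when results are reported.

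**Working it through.** The plan gives no figure to reproduce on this point. The check is a comparison of the control-arm text by setting, followed by a count of the measurements affected.

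**Control procedure by setting (Section 9)**

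| Setting | General rule | Setting-specific control text | Result |
|---|---|---|---|
| Preoperative wrist | Coconut oil | Measured with no intervention | Conflict on its face |
| During surgery | Coconut oil | None | No conflict |
| Recovery-room mask | Coconut oil | Coconut oil, same intervals | Agrees |
| Daytime floor wrist, 4-hourly | Coconut oil | No intervention | Conflict on its face |
| Night-time cotton ball | Coconut oil | None | No conflict |

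The conflict sits in 2 of 5 settings. The rubbing and breathing belong to both of them, because the floor application is "lavender oil on the wrist every 4 hours in the same manner as preoperatively".

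**Pain scores specified per patient**

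- Preoperative: 2 ("The level of pain will also be asked prior to application and at the second set of vitals").
- Recovery room: 3 ("pain score measurement will be taken 15, 30, and 60 minutes from lavender application").
- Floor: none specified.
- Total: 2 + 3 + 0 = 5.

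Of these, 1 precedes any application, 3 are taken in the matched recovery room, and 1 (the second preoperative score) follows a disputed application: 1/5 = 20%. Section 12 analyses change in pain without naming the time points, so it is not stated whether that score enters the comparison.

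**Daily ratings**

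Section 9 gives a typical stay of 1 to 3 days after surgery.

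- Satisfaction: 1 per day × 1 to 3 days = 1 to 3 ratings, all during the floor stay.
- Anxiety: 1 preoperative questionnaire, completed before any application and so unaffected, plus 1 to 3 during the floor stay.

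These counts show when the ratings are collected, not that they are biased.

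**Timing**

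- Preoperative vital signs are "monitored in the preoperative area before lavender is given and 30 minutes after it is given". Controls get two sets, but the interval between theirs is not stated.
- The extra floor set comes 45 minutes after each lavender application. No corresponding control set is written.
- The recovery-room text handles the same problem explicitly: controls are measured at the lavender arm's intervals, starting on arrival.

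**The case against.** The strongest reply is that the document resolves the conflict itself. Section 4 uses the word intervention for essential oil and, in the same sentence, has coconut oil applied. Read that way, the two later phrases mean only that no lavender is given. The general rule covers all five settings and states its purpose, the skin-irritation instruction presumes oil on control skin, and the disputed sentences stand in the measurement text rather than among the application instructions. Most of this stands: the shorthand reading is the more likely one. It does not close the point. Both sentences omit Section 4's qualifier, the recovery-room text between them names coconut oil, and the floor sentence sets applying lavender in one arm directly against doing nothing in the other.

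A reader might infer that controls have no time anchor at all. That is too strong. The preoperative application is placed half an hour before the operating room, controls are expressly given two preoperative sets, and the 4-hourly floor vital signs are not limited to one arm. What is missing is the control interval and an explicit 45-minute control set.

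It can also be said that the harm is doubly conditional: staff must take the literal reading, and brief rubbing, breathing and contact must affect the ratings. That is fair, and so is the remark that lavender's scent would remain. Section 4 describes the coconut oil as odorless, so matching the procedures would remove the difference in contact and exercise but not expectation from the smell.

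**Conclusion.** The wording conflict is real and should be fixed. It is confined to the preoperative and daytime floor settings, 2 of 5. The consequence rests on two assumptions: that some staff follow the sentences literally, and that the rubbing, breathing and contact influence what patients report. If so, daily satisfaction and anxiety could be confounded, and narcotic requests possibly. The documents give nothing from which to compute the size.

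Two stronger readings are tempting and are not supported. One is that the plan intends controls to receive nothing in these settings; Section 4 and the general rule point the other way. The other is that the postoperative pain comparison is compromised; the recovery-room scores are taken in a matched setting, and the single exposed score is preoperative. Nothing is claimed for sleep, since the night-time application is not contradicted.

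**What to change.** Reconcile Sections 4 and 9 to one control procedure, stated for each of the five settings and consistent with the plan's own aim of matching procedures between arms. Replace or define the two no-intervention phrases.

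In the same edit, time the second preoperative vital-sign and pain set, and the 45-minute floor vital-sign set, from the actual, charted application of study oil in each arm. Actual time is preferable to scheduled time because Section 9 has lavender applications charted so that vital signs can be related to time since application, and a late application would break that link.

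If controls already receive coconut oil under the general rule, the cost is wording, plus the 45-minute floor set if they do not already have it. Otherwise, it also includes a brief application at each daytime floor time point in controls. A 4-hourly schedule between 6am and 9pm gives at most 4 such time points per full day (for example 6am, 10am, 2pm and 6pm).
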